9.6.2 Approaches for increasing the response rate

Physicians are increasingly contacted to participate in web or phone surveys. Their overall response rate of participation remains low according to international studies (5)(6)(7). Holbrook et al. showed that the response rate to surveys continues to decline over time, but a lower rate does not appear to reduce the representativeness of a demographic survey (7). VanGeest et al. conducted a systematic review of 66 published reports on efforts to perform for improving response rates (8). Two general strategies were explored: incentives-based approaches and survey design-based approaches. Financial incentives, even little ones, were effective in improving physician response rates while non-monetary

incentives were much less effective. These measures include the use of a short questionnaire, and questionnaires personalized, and approved by professional associations.

In order to increase the response rate, three actions will be applied to this survey:

- A compensation fee will be proposed to physicians for their participation in the survey.
- All physicians will be sent an email or contacted by experienced operators of IMS Medical Radar with extensive experience in conducting health related surveys.
- Each physician will be emailed or called up to 3-5 times before being considered as “not reachable”, and reminders will be sent by email if IMS Medical Radar does not receive the web questionnaire.

9.7 DATA ANALYSIS

9.7.1 General statistical consideration

The statistical analysis will be conducted using the SAS® software V9.3 on Windows™ (SAS Institute, North Carolina, USA).

The statistical results of the twelve countries will be presented in the same report, overall, by country and per physician’s specialty group.

Table 3: Mock table to implement in the statistical and study reports

Country	Question 1...					All (unweighted)	All (weighted)
	ENT specialists	Ophthalmo- logists	Cardio- logists	Others (GPs, internists, geriatricians)			
Bulgaria	(N=xx)	(N=xx)	(N=xx)	(N=xx)	(N=xx)	(N=xx)	(N=xxx)
answer 1	xx (xx.x%)	xx (xx.x%)	xx (xx.x%)	xx (xx.x%)	xx (xx.x%)	xx (xx.x%)	xx (xx.x%)
answer 2	xx (xx.x%)	xx (xx.x%)	xx (xx.x%)	xx (xx.x%)	xx (xx.x%)	xx (xx.x%)	xx (xx.x%)
answer 3	xx (xx.x%)	xx (xx.x%)	xx (xx.x%)	xx (xx.x%)	xx (xx.x%)	xx (xx.x%)	xx (xx.x%)
Czech Republic	(N=xx)	(N=xx)	(N=xx)	(N=xx)	(N=xx)	(N=xx)	(N=xx)
answer 1	xx (xx.x%)	xx (xx.x%)	xx (xx.x%)	xx (xx.x%)	xx (xx.x%)	xx (xx.x%)	xx (xx.x%)
answer 2	xx (xx.x%)	xx (xx.x%)	xx (xx.x%)	xx (xx.x%)	xx (xx.x%)	xx (xx.x%)	xx (xx.x%)
answer 3	xx (xx.x%)	xx (xx.x%)	xx (xx.x%)	xx (xx.x%)	xx (xx.x%)	xx (xx.x%)	xx (xx.x%)
Estonia	(N=xx)	(N=xx)	(N=xx)	(N=xx)	(N=xx)	(N=xx)	(N=xx)
answer 1	xx (xx.x%)	xx (xx.x%)	xx (xx.x%)	xx (xx.x%)	xx (xx.x%)	xx (xx.x%)	xx (xx.x%)
answer 2	xx (xx.x%)	xx (xx.x%)	xx (xx.x%)	xx (xx.x%)	xx (xx.x%)	xx (xx.x%)	xx (xx.x%)
answer 3	xx (xx.x%)	xx (xx.x%)	xx (xx.x%)	xx (xx.x%)	xx (xx.x%)	xx (xx.x%)	xx (xx.x%)

Etc, for all participating countries

Overall - unweighted results	(N=xx)	(N=xx)	(N=xx)	(N=xx)	(N=xx)	(N=xxx)
answer 1	xx (xx.x%)	xx (xx.x%)	xx (xx.x%)	xx (xx.x%)	xx (xx.x%)	xx (xx.x%)
answer 2	xx (xx.x%)	xx (xx.x%)	xx (xx.x%)	xx (xx.x%)	xx (xx.x%)	xx (xx.x%)
answer 3	xx (xx.x%)	xx (xx.x%)	xx (xx.x%)	xx (xx.x%)	xx (xx.x%)	xx (xx.x%)
Overall - weighted results	(N=xx)	(N=xx)	(N=xx)	(N=xx)	(N=xx)	(N=xxx)
answer 1	xx (xx.x%)	xx (xx.x%)	xx (xx.x%)	xx (xx.x%)	xx (xx.x%)	xx (xx.x%)
answer 2	xx (xx.x%)	xx (xx.x%)	xx (xx.x%)	xx (xx.x%)	xx (xx.x%)	xx (xx.x%)
answer 3	xx (xx.x%)	xx (xx.x%)	xx (xx.x%)	xx (xx.x%)	xx (xx.x%)	xx (xx.x%)

Note: The table structure may be adjusted in the final study report.

All the analysis will be descriptive in nature and no statistical comparison will be done in this study.

Quantitative data will be summarized descriptively using n, mean, median, standard deviation, minimum and maximum. Categorical data will be summarized using frequency and percentage. 95% confidence interval (Wald's) may be constructed around the percentage values for some variables. Some of the variables may also be summarized by country.

Analysis for primary objective:

The proportion of targeted physicians who received, understood and agreed to implement the updated information about TMZ provided in the DHPC will be calculated. Analysis will be done in total and separately by specialty (ophthalmologists, ENT-specialists, cardiologists and others) using proportions and the corresponding 95% Wald confidence intervals).

Analysis for the secondary objectives:

The following variables will be analyzed separately for ophthalmologists, ENT specialists, cardiologists and others based on the information provided:

- proportion of prescriptions with the licensed indication will be summarized
- characteristics (age, gender) of patients to whom TMZ is prescribed will be summarized categorically.
- Data on type of TMZ prescribed (IR/MR/Oral Solution) will be summarized through frequencies and percentages.
- Proportion of cases where TMZ was prescribed as a combination / add-on treatment will be summarized through frequencies and percentages.
- Reasons for prescribing TMZ over other drugs will be summarized categorically.
- Timeframe to keep patient on TMZ will be summarized categorically.
- Discontinuation plan for the patients already on TMZ will be listed.

In a first step, calculations will be performed on raw data. No projection factor will be applied to generalize the results to the entire prescribers' universe. As a consequence, the line "Overall – unweighted results" will show only the results observed on the overall sample, and will not reflect the

countries' universe since this sample is not proportional to the size of the external list of physicians or IMS Medical Radar reference files in each country.

In a second step, the results will be weighted according to the real proportion of physicians in each country in order to accurately reflect the population that the survey seeks to measure.

For each country, the results will be reported according to the prescribers' specialty distributed proportionally to their weight within the IMS Medical Radar reference lists.

Possible selection bias will be assessed by comparing the distributions of available characteristics (e.g. region, age, gender, type of practice and specialty) between respondent and non-respondent physicians.

Handling of missing data:

The number of missing data will be indicated. Missing data will not be replaced by imputation methods. They are expected to be few and distributed at random.

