4.9 Data analysis

All analysis will be descriptive in nature and no statistical comparison will be done in this study. Results will be presented overall, by country and per specialty.

Quantitative data will be summarized descriptively using *n*, mean, median, standard deviation, minimum and maximum. Categorical data will be summarized using frequency and percentage. 95% confidence interval (Wald's) may be constructed around the percentage values for some variables. Some of the variables may also be summarized by country.

The proportion of targeted physicians who received, understood and agreed to implement the updated information about TMZ provided in the DHPC will be calculated.

All variables will be analyzed in total and separately for ophthalmologists, ENT specialists, cardiologists and others based on the information provided.

In a first step, calculations will be performed on raw data.

In a second step, the results will be weighted according to the real proportion of physicians in each country in order to accurately reflect the population that the survey seeks to measure.

For each country, the results will be reported according to the prescribers' specialty distributed proportionally to their weight within the IMS Medical Radar reference lists.

Possible selection bias will be assessed by comparing the distributions of available characteristics (e.g. region, age, gender, type of practice and specialty) between respondent and non-respondent physicians.

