9.5.2 Study size calculation

The sample size formula based on the normal approximation to the binomial is the following :

$$n = \frac{P \cdot (1 - P) \cdot (Z_{1-\alpha/2})^2}{e^2},$$

Where P is the expected proportion, e is one half the desired width of the confidence interval, and $Z_{1-\alpha/2}$ is the standard normal Z value corresponding to a cumulative probability of $1 - \alpha/2$ (e.g., if $\alpha = .05$ then $Z = 1.96$). As p is not known in advance, we consider it to be 50%. Such a hypothesis yields the most conservative i.e. largest sample size. If we consider a 2.7% precision and 95% confidence interval, we will need 1316 completed questionnaires.

For the conduct of survey, ideally the sample of 1316 physicians should be proportionally split between the selected countries based on the number of physicians in each country. However, due to large variance of the number of HCPs in targeted countries such a distribution would yield a too small number of interviews in smaller countries and would not allow the applicability of common statistical methods in those countries.

An empiric split of will be therefore implemented (

Table 2). Such sample will necessitate that the results of the study be weighted back according to the real proportion of physicians from IMS reference lists or available public information obtained through sources such as Eurostat (4) to order to allow the representativeness of the overall sample.

Usually, to ensure the robustness of statistical estimations at a given level of analysis (e.g. specialty or aggregated specialties per country), the sample size should not be lower than a threshold of 40 statistical units in each entity of this level. For analysis, less common specialties may need to be grouped. Subsequently, it will be necessary to weight back the study results according to the real proportion of physicians in order to determine the representativeness of the overall sample. In the event that the threshold of 40 statistical units (physicians per specialty in a country) would not be reached, then additional physicians of other groups will be recruited to compensate and preserve the sample size at country level.

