Based on IMS Medical Radar experience from previous similar surveys and estimates, about 10-15% of physicians will not complete the questionnaire because they do not know TMZ (the questions on prescribing conditions would not be applicable to them) or because they have to interrupt the interview due to an emergency (rare). Taking this into account, recruitment of physicians should continue until 1320 analyzable questionnaires have been reached.

Table 2: Number of analyzable physician interviews required per country

Country	Sample size objective
Bulgaria	100
Czech Republic	80
Estonia	80
France	160
Hungary	100
Latvia	80

Lithuania	100
Poland	120
Portugal	150
Romania	100
Slovakia	100
Spain	150
Total Sample Size	1320

Sample adjustment:

Since the relative weight of each country and of each specialty in the sampling plan is different from its real relative weight in the target lists, the extrapolation of the raw survey results to the overall target population would not be relevant.

A sample adjustment will be performed. The survey results will be weighted to reflect the real proportion of the two countries and within each country to reflect the real proportion of each specialty in order to extend the survey results to the overall target population. Both unweighted (i.e. raw data) and weighted results will be presented in the report.

A weight variable will be applied to each statistical unit (i.e. the analyzable physician) during the results calculation in order to correct any over-or under-sampling that may have occurred for a country or specialty. This weight variable will indicate how many unit(s) of the population of interest an observation will count in a statistical procedure. Its value will change per country and per specialty. The weights will be normalized to obtain their sum equal to the sample size.

In order to fill-in each stratum of the sample survey from the external list and the IMS Medical Radar file, an independent sample will be selected per stratum through a simple random sampling without replacement.

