9.7.3 Questionnaire analysis

The general statistical considerations described above (§9.7.1) will be applied for quantitative and qualitative variables. The number of missing data will be indicated. Missing values are expected to be few and distributed at random. Since there is no applicable method unanimously accepted, there will be no replacement or imputation of missing data (10).

Confidence intervals of 95% will be calculated for variables.

Physicians' answers will be analysed by subgroups of physician's specialty per country, and on the overall dataset.

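### Wald intervals combined with weights scaled to the sample size risk under-coverage for the weighted estimate, and for small specialty-by-country cells with extreme proportions

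*Protocol*

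**What the plan says.** Section 9.7.1 sets the primary analysis, in total and for the four specialty groups, as "using proportions and the corresponding 95% Wald confidence intervals". For other variables, section 4.9 (repeated in 9.7.1) is looser: "95% confidence interval (Wald's) may be constructed around the percentage values for some variables". Section 9.7.3 is firmer: "Confidence intervals of 95% will be calculated for variables". It then says answers will be analysed by "specialty per country, and on the overall dataset".

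Section 9.5.2 explains that a proportional split would leave too few interviews in small countries, so an empiric split (Table 2, 80 to 160 per country) is used and results are weighted back by country and specialty. On the weights it says: "The weights will be normalized to obtain their sum equal to the sample size". It describes each weight as the number of population units an observation stands for in a procedure. The same section gives the only variance expression in the document, P(1−P)/n, with P taken as 50%: "If we consider a 2.7% precision and 95% confidence interval, we will need 1316 completed questionnaires". It adds that "recruitment of physicians should continue until 1320 analyzable questionnaires have been reached". Section 4.8 attaches the 2.7% to the 1320.

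No section names a variance estimator for weighted proportions, a design effect, or an interval other than Wald.

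**The concern.** Section 9.9.3 says the results will be generalised to the target population only if the sample adjustment is applied. The weighted proportion is therefore the one that answers the primary objective. Weights that sum to n and are used as counts, put into the ordinary Wald formula, give p(1−p)/1320. That treats 1320 unequally weighted physicians as 1320 equally informative ones. A programmer following the text literally could produce this, and the interval would be too narrow whenever the weights vary much.

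The second issue is separate. Up to 48 country-by-specialty strata share 1320 physicians. A Wald interval in a cell of that size behaves badly when the observed proportion is near 0% or 100%: it can run outside the possible range or shrink to zero width.

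**Working it through.** **1. The plan's own figure.** n = P(1−P)z²/e² = 0.25 × 1.96² / 0.027² = 1317.4, against 1316 stated, which agrees for practical purposes. Table 2 sums to 1320. Half-width at 1320 = 1.96 × √(0.25/1320) = 2.70 points. This is a simple-random-sampling figure.

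**2. Weighted overall estimate.** Let W be a stratum's population share and q its sample share. If the true proportion is the same in all strata, and without a finite-population correction, the variance of the weighted proportion is p(1−p)/n × deff, with deff = Σ W²/q. Scaling the weights to sum to n does not alter deff. An interval that ignores deff has coverage 2Φ(1.96/√deff) − 1. The correct half-width at P = 50% is 1.96 × √(0.25 × deff/1320).

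q comes from Table 2. W is not in the protocol, so it is assumed over a range. The ratio-10 profile in full: France, Spain and Poland 10 each; Portugal, Romania, Czech Republic and Hungary 3 each; Bulgaria and Slovakia 2 each; the three Baltic countries 1 each; total 49. Then deff = (1320/49²) × Σ N²/n = (1320/2401) × 2.5925 = 1.425. The ratio alone does not fix deff, so the other rows are also illustrations of a profile.

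| Country weighting only (assumed profile) | deff | effective n | half-width, points | coverage if deff ignored |
|---|---|---|---|---|
| population proportional to (sample size)^1.5 or squared, i.e. near the sample split | 1.02 to 1.06 | 1300 to 1244 | 2.72 to 2.78 | 94.8% to 94.3% |
| largest:smallest = 5 | 1.18 | 1121 | 2.93 | 92.9% |
| largest:smallest = 10 | 1.43 | 926 | 3.22 | 89.9% |
| largest:smallest = 40 | 1.76 | 751 | 3.58 | 86.1% |

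Now add equal allocation to the four specialty groups, which the protocol does not state and is assumed here. With shares of 10, 10, 15 and 65%, the specialty factor is 4 × (0.01 + 0.01 + 0.0225 + 0.4225) = 1.86. With 5, 7, 8 and 80% it is 4 × (0.0025 + 0.0049 + 0.0064 + 0.64) = 2.615. With the same shares in every country, the factors multiply:

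- lowest of the 5 to 40 range: 1.178 × 1.86 = 2.19, half-width 3.99 points, coverage 81.5%
- highest: 1.758 × 2.615 = 4.60, half-width 5.78 points, coverage 63.9%

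**3. Small cells.** The mean cell is 1320/48 = 27.5. An equal four-way split gives 80/4 = 20 in the smallest countries and 160/4 = 40 in the largest. Holding 40 in every cell would need 48 × 40 = 1920 physicians.

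Exact coverage at n = 20, p = 0.95: the Wald interval contains 0.95 only for 16 to 19 successes. At 20/20 it is 100% to 100% and misses, with probability 0.95²⁰ = 0.358. At 15 or fewer it also misses, with probability about 0.003. Coverage is therefore 0.639. Other cases:

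| n | p | Wald | Wilson |
|---|---|---|---|
| 20 | 0.90 | 87.6% | 95.7% |
| 20 | 0.95 | 63.9% | 92.5% |
| 25 | 0.95 | 72.1% | 96.6% |
| 40 | 0.95 | 86.8% | 95.2% |
| 20 | 0.50 | 95.9% | 95.9% |
| 40 | 0.50 | 91.9% | 96.2% |
| 100 (one country) | 0.95 | 87.7% | 96.6% |
| 330 (one specialty, assumed equal split) | 0.95 | 93.4% | 95.8% |
| 1320 | 0.95 | 94.4% | 95.0% |

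**The case against.** A reader might infer that the protocol ignores the weights and that its intervals will be wrong. The text does not go that far. A Wald interval is an estimate plus or minus z standard errors, and the standard error may be design-based. Scaling the weights does no harm in that case. The P(1−P)/n expression stands in the sample-size section and is never prescribed for weighted results. The mock table shows counts and percentages only, and no sentence expressly attaches an interval to the weighted rows. A statistical analysis plan, not at hand, may name the estimator. These points stand, and they make the weighted part conditional.

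A reader might also take coverage of 64% to 81% as the expected result. That needs equal specialty allocation, which is not stated, and specialty shares that are not given. Stratification gains and a finite-population correction generally act the other way.

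On small cells, the primary-objective sentence covers only the total and the pooled specialties, where unweighted Wald coverage is 93% to 95% for p from 0.05 to 0.95. Section 9.7.3 does not say that every cell receives an interval. Failure needs a small cell and an extreme proportion together. Licensed use by specialty would be a poor example: its unit is the prescription, it is only summarised, and no interval is named for it.

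The safeguards in section 9.5.2 do not answer the point. The 40-unit threshold can be met by grouping specialties, but a shortfall may also be filled from other groups, and at n = 40, p = 0.95 coverage is still 87%. The warning about subgroup intervals concerns their precision, not their coverage.

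**Conclusion.** The concern holds in conditional form. The protocol fixes Wald limits and n-scaled weights for a disproportionate sample and offers no variance other than the simple-random-sampling one. If that variance is used for the weighted overall proportion, coverage falls to about 93% to 86% under country weighting with assumed ratios of 5 to 40. It falls further, to about 81% to 64%, only under the added specialty assumptions, and stays near 95% if population shares are close to the sample split. Whatever variance is programmed, the 2.7% precision does not carry over: the half-width is about 2.9 to 3.6 points in the first case and 4.0 to 5.8 in the second, with equal stratum proportions and no finite-population correction.

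Independently of the weights, any Wald interval for a specialty-by-country cell is unreliable near 0% or 100%. The unweighted total and pooled specialties are sound. Point estimates are unaffected, and the study is descriptive with no success threshold, so what is at risk is the stated uncertainty.

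**What to change.** - For every weighted result, state a stratified design-based (Taylor-linearised) variance with country × specialty as strata, the sampling weights, and stratum totals for the finite-population correction. Use logit or modified Wilson limits. The SAS survey procedures are the natural tool.
- For unweighted country and specialty-by-country cells, replace Wald with Wilson or exact limits. Wald may stay for the unweighted total and pooled specialties.
- Report the achieved design effect beside the weighted primary estimate.
- In sections 4.8 and 9.5.2, say that the 2.7% precision applies to the unweighted sample only.

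The cost is minor programming and somewhat wider weighted intervals. No new data are needed.

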9.7.2 Analysis of non-participation or refusal to participate rate

As often required by the Authorities, the following different cases of total non-response will be distinguished and analyzed:

- Targeted physicians: Physicians reached to whom an email or mail has been sent, or have been called.
- Contacted physicians: Physicians who have been reached out by phone or have opened their email (if the score is technically available in their country).
- Physicians who agreed to participate: Physicians willing to participate in the survey (e.g. by phone or by clicking on the link provided in the recruitment email).
- Physicians with complete questionnaire: Physicians who actually completed the questionnaire until its end.

The physicians' participation in the survey will be examined via different ratios:

- Contact rate = contacted physicians / targeted physicians
- Response rate = Physicians who agreed to participate / contacted physicians
- Cooperation rate = Physicians with complete questionnaire / Physicians who agreed to participate
- Refusal rate = contacted physicians - physicians who agreed to participate / Physicians reached

The reasons for non-response will be sought, especially from all observed variables. This will ensure that missing data are reported with enough detail to strengthen the results validity, as recommended by the STROBE guidelines (9).

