9.2.2 Exclusion criteria

Inactive and retired physicians (when documented information is available to identify them) will be deleted from the contact lists before randomisation.

The following exclusion criteria will be checked at the beginning of the web-questionnaire:

- Physicians who do not treat patients or who may have a conflict of interest (i.e. physicians employed by regulatory bodies or pharmaceutical industries),
- Physicians who do not know TMZ

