9.9 LIMITATIONS OF THE RESEARCH METHODS

9.9.1 Possible selection bias due to voluntary participation

The selection bias of physicians participating in a survey is an inherent bias to any study based on volunteer participation. In order to quantify any selection bias, the distribution of each stratification criterion of healthcare professional (country and specialty) will be compared between participants and non-participants.

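### The cooperation rate in section 9.7.2 keeps physicians screened out as ineligible in its denominator, so ineligibility is reported as lack of cooperation

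*Protocol*

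**What the plan says.** Section 9.7.2 sets up four nested groups (targeted, contacted, agreed, complete) and builds participation ratios from them. The one at issue is "Cooperation rate = Physicians with complete questionnaire / Physicians who agreed to participate".

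- **Denominator.** Those who agreed are "Physicians willing to participate in the survey (e.g. by phone or by clicking on the link provided in the recruitment email".
- **Numerator.** Those who are complete are "Physicians who actually completed the questionnaire until its end".
- **Timing of screening.** Section 9.2.2 states: "The following exclusion criteria will be checked at the beginning of the web-questionnaire". The criteria are not treating patients, a conflict of interest, and "Physicians who do not know TMZ".
- **Expected loss.** Section 9.5.2 foresees that "about 10-15% of physicians will not complete the questionnaire because they do not know TMZ". The same sentence adds interruption by an emergency as a second cause, described as rare. It follows that "recruitment of physicians should continue until 1320 analyzable questionnaires have been reached".
- **Database check.** Section 9.8.2 plans two separate estimates: the percentage of physicians who do not know TMZ, and the percentage without a complete analyzable questionnaire.
- **Selection bias.** Section 9.7.1 compares respondents with non-respondents. Section 9.9.1 says that "the distribution of each stratification criterion of healthcare professional (country and specialty) will be compared between participants and non-participants". Neither section defines its two groups.

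**The concern.** Section 9.7.2 is meant to separate the different kinds of non-response so that the validity of the results can be judged. Being ineligible is not non-response. An eligible physician who breaks off is non-response, and can bias the results. The formula puts both in one figure, and by the protocol's own expectation ineligibility is the larger part of it. A low cooperation rate could then be read as reluctance among eligible physicians when it mainly reflects how many invited physicians do not know the drug. If that share differs between specialties or countries, cooperation rates compared across them would differ for the same reason.

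An SAP might add detail, but the protocol already states the formula explicitly, so this is not a matter merely left open for later.

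**Working it through.** **Inputs.** Target of 1320 analyzable questionnaires and non-completion d = 10-15% (both section 9.5.2); definitions from 9.7.2; timing of screening from 9.2.2.

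**Step 1: the plan's own figure.** n = P(1 − P)z²/e² with P = 0.5, z = 1.96 and e = 0.027 gives 0.25 × 3.8416 / 0.000729 = 1317.4. The protocol states 1316 and sets a target of 1320. The difference is trivial, and the country targets in Table 2 add up to 1320. The protocol gives no expected cooperation rate, so there is none to reproduce; its implied value is derived below.

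**Step 2: path of a screened-out physician.** The physician clicks the link and is counted as agreed. The questionnaire opens, the exclusion check fails, and the end is not reached. The contribution is 1 to the denominator and 0 to the numerator. None of the four groups in 9.7.2 is for ineligible physicians, and the list in 9.6.1 of when a physician counts as contacted has no such outcome either.

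**Step 3: rate as defined.** Take the 10-15% as a share of those who agreed (an assumption, since 9.5.2 does not name its base). Agreed = 1320/(1 − d).

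- d = 10%: 1320/0.90 = 1467 agreed, 147 not complete, rate 1320/1467 = 90.0%.
- d = 15%: 1320/0.85 = 1553 agreed, 233 not complete, rate 1320/1553 = 85.0%.

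**Step 4: rate with ineligible physicians removed.** Rate = 1320/(agreed − ineligible), where ineligible = s × (agreed − 1320). The share s is not given in the documents, so a range is shown. The understatement is in brackets.

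| s | d = 10% | d = 15% |
|---|---|---|
| 100% (upper bound) | 1320/(1467 − 147) = 100% (10.0 points) | 1320/(1553 − 233) = 100% (15.0 points) |
| 80% (assumed) | 1320/(1467 − 117.6) = 97.8% (7.8 points) | 1320/(1553 − 186.4) = 96.6% (11.6 points) |
| 50% (assumed) | 1320/(1467 − 73.5) = 94.7% (4.7 points) | 1320/(1553 − 116.5) = 91.9% (6.9 points) |

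**Step 5: with real break-off added.** Suppose the whole 10-15% is ineligibility and a further 10% of eligible physicians drop out (assumption). The formula gives 0.90 × 0.90 = 81.0% or 0.85 × 0.90 = 76.5%, against a true 90% among eligible physicians.

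**Step 6: selection-bias comparison.** The response rate in 9.7.2 is agreed over contacted, so a physician who clicked counts as a response there. Sections 9.7.1 and 9.9.1 use undefined pairs of terms. The text therefore does not assign screened-out physicians to either side.

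**The case against.** The strongest reply is that the missing information is already planned. Section 9.8.2 estimates separately the share who do not know TMZ and the share without a complete analyzable questionnaire, and 9.7.2 says that reasons for non-response will be sought. A reader could correct the overall rate by hand. This stands in part. It covers the main ineligibility reason, but 9.8.2 does not link the estimate to the ratio, does not ask for it by country or specialty, and gives no separate count for the other two exclusions. The rate would still be published uncorrected.

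It is also fair to say that no threshold, weight or estimate depends on the cooperation rate. That stands, and it limits the point to participation reporting.

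The 10-15% pools ineligibility with interruptions, so it would be wrong to state as fact that full cooperation by eligible physicians would appear as 85-90%. That is the upper bound.

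A reader might infer more: that screened-out physicians enter the selection-bias comparison as non-participants and create a false specialty imbalance. The documents do not support this. The groups are undefined, and the response-rate definition points the other way if anything. Even on that reading the effect could be small. With an assumed response rate of 10-20%, about 5,900 to 14,000 contacted physicians would not have agreed, and 147-233 non-completers would be roughly 1-4% of the non-participant group. At an assumed 50% they would be 9-13%.

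**Conclusion.** The point holds as a defect in one reported rate. Under 9.2.2 and 9.7.2, a physician screened out inside the questionnaire lowers the cooperation rate although no lack of cooperation occurred. On the figure in 9.5.2, the understatement is at most about 10-15 points, about 8-12 points if 80% of non-completion is ineligibility, and about 5-7 points if half is. These sizes assume that the 10-15% applies to physicians who agreed. Section 9.5.2 does not mention the exclusions for not treating patients or for conflict of interest, and no figure is available for them, so they are not sized.

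For the selection-bias comparison, the supportable finding is only that the place of screened-out physicians is undefined. The primary proportion, its confidence interval and the sample size do not change.

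**What to change.** In section 9.7.2:

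- Add an outcome for physicians who agreed but were ineligible at screening.
- Define the cooperation rate as complete questionnaires / (agreed − screened out as ineligible).
- Report the ineligible share by country and specialty, with the reason for exclusion. This extends the estimate already planned in 9.8.2.
- Note that physicians who agreed by phone but never opened the questionnaire remain in the denominator with eligibility unknown, and give their number.

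In sections 9.7.1 and 9.9.1, define respondent and participant, and show screened-out physicians as a separate group.

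The cost is one changed formula, one added category and a sentence or two of definition. The questionnaire must obtain the screening answers anyway in order to apply 9.2.2. The protocol implies that the answer on knowing TMZ is kept, but does not say so for the other two exclusions, so the sponsor should confirm that all three outcomes are stored.
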